# A. Introduction and Background

It is clear that the COVID-19 pandemic has impacted families adversely in multiple ways, including economic stressors (e.g. changes in employment status or functioning), mental health-related functioning (including depression and suicide-related behaviors), social/familial functioning (including parenting and risk for domestic violence), as well as responses to mandated safety measures (e.g. social distancing, stay-at-home orders, mask-wearing). Furthermore, families of school-age children have had to navigate online instruction and home schooling in the context of these difficult circumstances with little preparation for doing so effectively. School districts have varied widely in their ability to support parents during this crisis. These stressors are likely to have disproportionately adverse effects on lower-income and racial / ethnic minority populations, for whom economic, academic, and family-level challenges were already pronounced. For instance, health effects of COVID-19 have hit African American and Latinx populations with disproportionate severity, including higher rates of hospitalization and death (Garg et al., 2020). Given the scale of pandemic impacts for families with school-aged children, the identification of effective family-focused interventions that target core mechanisms of change with a broad range of benefits for parents and youth across diverse populations, and that can be brought to scale rapidly and with fidelity, represent critical public health goals.

This supplement will adapt and test the efficacy of the Family Check-Up Online as a treatment to foster resilient family functioning in response to the COVID-19 pandemic. We will test the effects of the adapted FCU Online program on key mechanisms of change, including parenting skills, parental depression, and parent/child self-regulation, that we predict will directly impact child and family functioning. We predict that changes in these key targets of the intervention will impact participant's response to the COVID-19 pandemic, including youth depression and behavior problems, the ability to cope with pandemic-focused stressors (e.g. dealing with changes in employment status or functioning; following mandated safety measures), and social/familial functioning (including relational support and risk for domestic violence).

# **B.** Specific Aims/Study Objectives

toolbox.

Aim 1: Adapt the FCU Online for low-income parents of school-age children in response to the Covid-19 crisis. Our team will use a formative development process of adaptation to develop a new module and test existing content for the FCU Online derived from the FCU Online for middle school and the FCU Online for young children. Both of these programs draw from the original content of the FCU developed by Dishion and [name] and the Everyday Parenting. Modules developed as part of the FCU Online include positive parenting, limit setting, proactive parenting, healthy routines, monitoring/supervision, and parent wellness. New content developed for this supplement will include stress management and coping with pandemic-related disruptions (e.g. economic challenges, social distancing and isolation), supporting learning at home, and effective parenting practices in the context of pandemic (e.g. managing quarantine/social distancing). We will examine usability and acceptability through focus groups with stakeholders, schools, and parents (N=20).

Aim 2: Conduct a pilot test of the efficacy of the adapted FCU Online developed in Aim 1. Our team will conduct a pilot study to test acceptability and feasibility of our approach (n=180) that includes a pre- and post-assessment in a waitlist, controlled design. Assessments will include measures of mental health (children and parents), stress (children and parents) and problem behavior (children) as well as a range of risk factors using measures adapted for COVID 19 from the NIH

Aim 2a: Evaluate FCU effects on proximal mechanisms. In line with the experimental therapeutics approach to treatment development, we will examine the extent to which the FCU targets the three hypothesized mechanisms, including reductions in parental depression, improvements in effective parent management practices, and improvements in parent and youth self-regulatory abilities.

Page 1 of 14 Version Date: 1.20.2024

Aim 2b: Evaluate FCU effects on targeted parent/youth outcomes at post-treatment and follow-up, and examine mechanistic pathways via mediation analyses. We will examine FCU effects on core targeted outcomes at post-treatment and follow-up, and will conduct mediation analyses to examine whether hypothesized mediators explain intervention effects on targeted outcomes. We predict that the FCU will predict improved parenting skills, reduced parental depression, and improved self-regulation, which in turn will predict reduced youth depression and problem behavior, as well as improved parent and youth coping with COVID-19.

# C. Methods, Materials and Analysis

This project includes several phases of research that involve different groups of participants who are recruited and consented at different times and in different ways. We have included a chart to help orient the reader to the sequence and timing of these phases. More detail about the method for each of these phases of research appears below.

Phase	Timing	Research Participants	Status
1. Formulate research procedures, network with community organizations for possible participation, program app, develop survey instruments	October 2020-July 2021	n/a	completed
2. Focus groups with staff of community agencies and parents	July 2021	staff N=8; recruited from organizations selected in Spring 2021.  parents N=16; recruited from community. There will be 2 groups of parents, one Spanish-speaking and one English-speaking.  Participation will last one hour.	completed
3. Pilot Study	September 2021- November 2022	N=180 families with children aged 10-14 recruited from the community over 6 months. Participation will last 6 months.	completed

### Focus Groups (N=24)

During the first 9 months of the study, we will design an interactive, engaging, app based on the Internet version of the FCU. Although the app version will be based upon the internet version of the FCU (and the in-person model of treatment), our development work will be guided by iterative formative research that includes use of focus groups. Three focus groups will include Spanish-speaking parents, English-speaking parents, and personnel from community agencies who work with children and families similar to those targeted by this intervention (up to 8 per group for a total of 24 users). Focus groups will be used to elicit ideas and opinions about the content, structure, and aesthetic design of the app. Focus groups will be conducted via a HIPAA-compliant version of Zoom. Focus groups will be presented with a mock-up of the "Positive Parenting" module of the app and facilitators will solicit their feedback about the proposed approach and general features. During these sessions, facilitators will follow a written guide to ensure that key topics are covered, probe for thoughts and attitudes, and encourage participation from all participants. Focus groups will be recorded via Zoom; the recording will be recorded to a facilitator's work computer and transcribed. Transcripts of sessions will be coded to enable content analysis

Page 2 of 14 Version Date: 1.20.2024

of salient constructs, issues, and language use that contribute to the program features and functions. Participants' comments will guide us in terms of preferences for video models, language level, text elements, and programmatic tone.

Parent focus groups will begin with an overview of the FCU Online program, including the purpose of the app and its proposed structure. This would include coverage of the three main elements of the app: assessment, feedback, and parenting skills training modules that include brief videos and animations and interactive elements. This overview will also highlight the role of the consultant. Mock-ups of selected pages of the app will be presented, including a welcome page and the FCU assessment, feedback, and skills training elements of the "Positive Parenting" module. At various points, participants will be asked a series of questions designed to elicit opinions and set the occasion for group discussion (see "questions for parent focus groups\_5.25.2021"). At the end of the session, participants will be asked to describe their overall reaction to the proposed features of the program. Candid opinions will be encouraged including what participants did not like as well as any features they thought were missing and should be added.

Focus groups with staff of community agencies will begin with the same overview of the FCU Online program described above, pausing periodically to ask questions designed to elicit opinions about the program and app (see "Questions for provider focus groups\_5.25.2021"). At the end of the session, participants will be asked to describe their overall reaction to the proposed features of the program. They will also be asked their opinion on how well this program would "fit" in their agency and how we might enhance that fit.

## Pilot Study (n=180 families)

We will recruit and randomly assign 180 families with school aged children between the ages of 10 and 14 to one of two conditions: (a) FCU intervention (n=90), or (b) a waitlist control group (n=90) that will receive school/ community resources as usual and then offered the intervention immediately after completing the 4-month assessment. This design will enable us to evaluate FCU effects on targeted parent/ youth outcomes. Participation in this study will be 6 months for all families, regardless of condition.

The FCU preventive intervention historically has been delivered in face-to-face sessions between family consultants and parents. Family consultants would do motivational interviewing to determine existing concerns in the family, and motivate parents to make positive change in their parenting and family dynamics. They would provide feedback on the family assessment, and offer coaching and/ or resources to help parents make desired changes. The FCU intervention is intended for prevention, not treatment, of serious youth behavior and to promote growth in positive school and social behaviors. For this project we have developed a computer app that scores family assessments, provides feedback, and provides skill-building content similar to what was previously offered to parents face-to-face. In this project, parents will use this app and receive individualized coaching over the phone or Zoom (depending on parent choice). Throughout this document the word "telehealth" is used to refer to this "app + remote coaching" mode of delivery. The app is not "intended for use in the diagnosis of disease or other conditions, or in the cure, mitigation, treatment, or prevention of disease in man." However, the coach-parent relationship may offer therapeutic benefits.

Families will be recruited from local middle schools and community organizations that serve low-income families. We will provide English and Spanish fliers to agencies and schools to distribute within their communities as they see fit. These fliers will refer potential participants to our recruitment website (www.middleschoolstudy.org), which has content in both Spanish and English. People who are interested in participating will fill out a form on the website indicating their name, phone number, and a good time to reach them. Responses to this form will be deposited in one of two project email accounts, where either an English or Spanish-speaking recruiter will retrieve them and attempt to call interested parents at the desired time. At the time of recruitment, the recruiter will determine eligibility for the study, preferred language for participation, review the key elements of the consent form, and answer parent's questions about the study. If the parent indicates willingness to participate, they will be emailed a link to a consent form in Qualtrics. They will confirm their consent to participate by typing in their name and date in the appropriate fields on the form. At the time of this phone call the recruiter will also determine if the parent has access to the web via a computer or tablet, or just with a smartphone. If they only have a smartphone, they will be scheduled to complete their parent survey as an interview because we have determined that the survey is too difficult to respond to on a smartphone. If they have access to a computer or tablet, we will ask their preference between completing the survey on their own or as an interview. Parents who choose to complete the assessment on their own will receive an email that includes a personalized link to a Qualtrics baseline assessment and a "special word," a four-letter word that will function as their unique ID for the study but is easier to remember than a standard participant ID number. Parents who choose to complete it as an interview will be scheduled for a phone or Zoom

appointment in order to complete it. Zoom will be the default choice for interviews unless parents' access to technology, data plans, etc., require the phone option. Similarly, youth will have the choice to complete their data collection via Qualtrics survey or in an interview format via Zoom or phone. Youth who chose to complete surveys on their own will complete the assent process over the phone prior to receiving a link to the survey. All Zoom interviews will take place via a HIPAA-compliant account to ensure confidentiality. During this Zoom call, a research assistant will share their screen, go over the assent form, and answer any questions posed by the youth. If the youth assents to participation, the research assistant will check a box on a Qualtrics assent form indicating they obtained youth assent, and type in the child's name, the date, and their own name. The baseline assessment includes standard, widely-used questionnaires that ask questions about the child's abilities and behavior, parenting practices, family dynamics, family demographics, family health behaviors, and life stressors. The parent assessment takes about 45 minutes to an hour to complete; the youth survey takes about 30 minutes. Data collection interviews that occur via phone or Zoom will not be recorded.

The youth survey contains a few items regarding depression and thoughts of harming the self. We have developed a protocol to handle the cases in which youth respond that they have thoughts that they would be better off dead, or of hurting themselves in some way. Each day, research staff will be assigned to review all youth assessments that are completed as surveys. If a research assistant discovers that a youth has responded to this item with any response choice other than "not at all," they will immediately notify the Family Consultant on duty, who will reach out to the youth by phone to ask a few scripted follow-up questions to gather information, assess imminent danger, and to build rapport with the youth. They will also develop a safety plan if there is current risk of self-harm. This safety plan would include informing the parent, so that they can be involved in getting support for their child. For youth who complete the assessment as an interview, the youth will be responding to this item verbally. If the youth responds anything other than "not at all" to this item, the research assistant will finish the interview, and immediately notify the Family Consultanton duty that they will need to speak to the participant. If, during an interview, the youth divulges suicide ideation without a prompt, the research assistant will ask a few scripted follow-up questions, complete the interview, and then let the participant know that a Family Consultant will be coming onto the session to ask a few more follow –up questions. Once the Family Consultant is on the call, the RA will leave the session so that the participant and family consultant can talk privately. The family consultant will then follow-up individually with the youth and conduct the suicide risk assessment described above. They will develop a safety plan if there is current risk of self-harm. This safety plan would include informing the parent, so that they can be involved in getting support for their child.

Because assessments are completed via Qualtrics, we will be able to track how quickly participants are completing the survey. If they have not yet completed the survey one week after receiving the link to the survey, a paid staff member will call the caregiver to see if the caregiver has any questions about the survey and remind them to complete it as soon as possible.

Once surveys/ interviews are completed, participating families will be randomly assigned to one of two conditions (intervention or waitlist control). Parents in the **intervention condition** will be contacted by a Consultant to schedule an initial phone or Zoom session in which the coach shares information about the FCU Online process, gathers some information from the parent, and motivates the parent to engage in the program. Parents will have the choice whether to complete these sessions over the phone or Zoom. Either way, sessions will be recorded via Zoom in order to evaluate consultants' fidelity to the intervention model (i.e., how well the consultant adhered to each element of the Family Check-Up model during their appointments with a given parent). If a parent chooses to complete these sessions by phone, the consultant will put the parent on speaker phone and start a Zoom "meeting" with themselves, recording the meeting. The only image that would be appear in this recording is the consultant's black screen. After the meeting is over, the video portion of the recording would be deleted while retaining the audio file. If a parent chooses to complete the meeting via Zoom, the meeting will be recorded. It is likely that both the parent's image and the consultant's image would be recorded (assuming they both choose to share their video), but, again, the video portion would be deleted after the meeting is over and only the audio file would be retained. After the initial meeting is over, Parents will receive an email that includes information about how to log in to the app. Participants in the **waitlist control group** will receive an email thanking them for their participation and letting them know that they will next be contacted by project staff in 2 months.

Participants in the **intervention condition** will log in to the FCU app where they will complete the first module, which includes a brief 5-minute assessment, feedback on their data, and online tools to support their parenting in areas that were identified as challenges by the assessment (see fuller description below under "Content of Skills Sessions and Web/ Mobile

Activities"). These tools include videos, animated videos, parenting tips, and interactives. Parents will also be given the opportunity to practice parenting skills. Parents will be able to log-in as often as they like and interact with any of the parenting Skills Sessions on the app. In addition, a Consultant will contact them after completion of the first module to talk through their results, help them set goals, offer support over the phone/ Zoom, and help motivate parents to improve parenting practices. Parents will be able to contact their Consultant as often as they like and will have at least 5 scheduled phone sessions with a consultant (i.e., one after the completion of each module). We anticipate that each of these checkins might take around 20 minutes, but will adapt to the needs of the family. Each of these sessions will be recorded via Zoom, as described above.

Caregivers in both conditions will be invited to participate in follow-up questionnaires at 2 months, 4 months, and 6 months after baseline. This survey will be identical to the baseline assessment so that we can evaluate change over time in the assessed constructs. Parents will once again have options regarding completing the survey on their own or as an interview, via Zoom or phone. Youth data will only be collected at baseline and 6 months after baseline. Youth will also have the option to complete the survey on their own or as an interview over Zoom or phone. The estimated time needed for parents to complete each of these follow-up questionnaires is 45 minutes to an hour; the estimated time needed for youth to complete each follow-up interview is 30 minutes. At the time of the 2-month follow up, parents in the intervention condition will also complete a 2-page FCU Online Satisfaction Survey. This survey will also be completed via Qualtrics.

All families will be compensated for their time. Parents will receive \$75 for completing assessments at baseline, 2 months, 4 months, and 6 months for a total of \$300. Youth with receive \$25 for completing assessments at baseline and 6 months, for a total of \$50.

**FCU intervention protocol.** The FCU app being developed for this research study will motivate caregivers to use positive parenting skills and effective communication with their adolescent to reduce family conflict and subsequent problem behavior. The original FCU takes place in person and involves at least three sessions, including (a) an initial rapport-building interview, (b) an assessment with the caregiver(s), and (c) a feedback session during which the results of the assessment and initial interview are discussed with the caregivers, attention is focused on the caregivers' readiness to change, and specific change options are delineated. The feedback session is both strengths-based and specific. The goals of feedback sessions are to (a) share assessment findings with caregivers regarding areas of strengths and challenges, (b) engage in a motivationally enhanced discussion about promoting positive changes, and (c) provide a menu of resources to facilitate the family change process. Emphasizing areas of strengths and challenges reduces parents' defensiveness and enables them to feel empowered to pursue strategies for making changes relevant to their family's needs. At the end of the feedback session, a menu of interventions is presented and discussed collaboratively with the caregivers.

In this study, families in the intervention condition will be contacted by a consultant for an initial phone session after research staff receive their completed baseline assessment. This phone session will serve as the "initial interview" for these parents and will allow the consultant to share information about the FCU Online process, gather information from the parent about concerns for their child or parenting goals, and to motivate parents to engage in the program. After the initial interview, parents will receive an email invitation to log into the FCU app with their name, email address, and smartphone number. This information allows parents to create a page that is exclusively viewed by the parent or parents who choose to participate. Parents will be directed to login and complete the first module of the online assessment. They will complete a brief (5-min) assessment of parenting skills in the focus area, and then receive immediate feedback in written format, generated by the app program. Web programmers have created algorithms that generate the feedback, highlighting family strengths and areas of growth. After parents receive feedback, they will be directed towards content designed to help them build parenting skills in the specific content area. The skills sessions in each parenting module are guided by our Everyday Parenting curriculum. The skills sessions will consist of content and structured activities that are designed to help parents learn each skill.

After completing the first module, parents will discuss the feedback and skill-building content with their consultant via phone or video conferencing. The consultant will provide supportive feedback, help parents set goals in terms of intervention targets, and arrange to check in with the parent about the next module. There are 5 skills modules, and parents will follow the 4-step process of assessment feedback skills session consultation for each module. The first check-in will occur after one module of the parenting curriculum has been completed, or after 2 months, whichever comes first. Additional meetings may be scheduled as needed. These meetings will be audio or video recorded and sessions will be evaluated for the consultant's fidelity to the intervention model.

Page 5 of 14 Version Date: 1.20.2024

There is no youth component to the online assessment.

After completing the FCU, families will continue to participate in the post-tests previously described. These post-tests occur at 2, 4, and 6 months after the baseline assessment for parents, and at 6 months after baseline for youth. At the end of the 2 month post-test assessment, parents will also be asked to complete a FCU Online Satisfaction Survey. This questionnaire will assess satisfaction with the content and delivery of the model and factors related to uptake and usage of the information. This questionnaire will be completed via Qualtrics. Participants will receive an email with a link to complete their survey. It should take about 10 minutes to complete.

Content of Skills Sessions and Web/Mobile Activities. On the basis of assessment results, parents will be offered a variety of follow-up parenting skill activities. Each of the skills sessions, derived from our Everyday Parenting curriculum (Dishion et al., 2011), will include content that is animated, video based, and interactive. They will each include activities for tracking of behavior and will provide ongoing feedback to parents on their success. Each skills session will also highlight behaviors that target school success at this age, including homework completion, attendance, and home-to-school planning. A description of the skills taught in each of the 5 modules is provided below.

**Healthy behaviors for stressful times.** This module focuses on teaching parents both the importance of, and how to support their child in, 7 areas of their child's life: emotional well-being, coping with stress, social connections, eating, body image, physical activity, and "screens" (traditional media, social media, phones, etc.).

**Positive parenting.** Four teaching content areas will focus on positive behavior support: encouragement and praise, spending quality time, giving directions, and using incentives for positive behavior. The "encouragement and praise" content area shows parents how to develop skills for using positive language with their adolescent. The "spending quality time" area encourages parents to see spending time together as a way to build a happier, healthier relationship. The "giving directions" area helps parents understand and learn basic skills for promoting behavior change in their child. The "using incentives" content area helps parents develop skills for using incentives and planning how to manage their child's behavior.

**Rules & consequences.** This skills session includes establishing clear rules, monitoring, limit setting, identifying appropriate consequences for behavior, and ignoring annoying behavior. The "clear rules" area shows parents how to establish clear commands and expectations and asks parents to track both desired and undesired behaviors over time. "Monitoring" encourages parents to keep track of their child's behavior, especially when they are not with them. "Identifying appropriate consequences" includes working with the adolescent to develop incentives and consequences that are meaningful to reduce negative behavior and increase positive behavior. "Ignoring" encourages parents to not react to behaviors that are merely pestering/ annoying.

**Support School Success.** This content area will provide useful guidance to parents in how to establish healthy home routines (related to meals and sleep), and how to support their child's success in school (getting to school on time, organizing homework, and supporting homework). A number of activities to help parents develop these skills will be available.

**Communication.** The "communication" area teaches active listening skills and effective problem solving and negotiation skills.

Training and Monitoring of Consultants. Consultants will be trained in the FCU, motivational interviewing, and school-based interventions. A lead consultant will oversee training and supervision of at least two other consultants who will also serve as the consultant for some of the participants, to decrease bias in the intervention. All consultants will be trained, supervised, and supported to help them effectively implement the FCU. The supervising consultant and two hourly consultants will be trained to reach a minimum level of competence via in-vivo role-play. Feedback with pilot families will be recorded and rated by the clinical supervisors using the COACH fidelity of implementation rating system (Dishion et al., 2010). A 9-point scale is used to rate each of the following dimensions: (a) Conceptual adherence to the FCU model, (b) Observant and responsive to family concerns, (c) Actively structures sessions for optimal behavior change, (d) Carefully teaches when appropriate, and (e) Hope and motivation are generated. Consultants are guided for the first two to three cases until they attain minimum fidelity standards; guidance is repeated quarterly. A series of studies has shown greater fidelity to the FCU is associated with improved parenting practices and reduced youth behavior problems in families with young children (Smith, Dishion, & Knoble, under review; Smith, Dishion, Shaw, et al., 2013).

Page 6 of 14 Version Date: 1.20.2024

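### Do the two accounts of consultant contact conflict, and does the two-month post-test come too early to follow the programme?

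*Combined protocol and SAP*

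**What the plan says.** In Section C, the Pilot Study text says that parents in the intervention arm "will have at least 5 scheduled phone sessions with a consultant (i.e., one after the completion of each module"). On length it adds: "We anticipate that each of these checkins might take around 20 minutes".

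The FCU intervention protocol, later in Section C, describes five skills modules, each worked through as assessment, feedback, skills session and consultation. After the first module the consultant is also to arrange the contact about the next one. It then says: "The first check-in will occur after one module of the parenting curriculum has been completed, or after 2 months, whichever comes first". The next sentence is "Additional meetings may be scheduled as needed".

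The post-tests are introduced with "After completing the FCU, families will continue to participate in the post-tests previously described", and the sentence after that dates them at 2, 4 and 6 months from baseline for parents and 6 months for youth. The only nearby description of what an FCU consists of concerns the face-to-face version: "The original FCU takes place in person and involves at least three sessions".

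The Data analytic plan analyses all families by assigned arm whatever they received. It names 2 and 4 months as the waves of main interest and plans a descriptive summary of engagement, giving web visits as an example.

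**The concern.** Three things catch the eye.

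- **Number of sessions.** If "Additional meetings may be scheduled as needed" covers everything after the first check-in, the second account guarantees one post-module session where the first guarantees five.
- **Order of delivery and assessment.** A first check-in that may fall as late as 2 months fits badly with a 2-month post-test said to follow completion of the programme, and completion is not defined. Aim 2b refers to post-treatment effects without naming a wave.
- **No count of what was delivered.** Fidelity coding assesses "how well the consultant adhered to each element of the Family Check-Up model during their appointments with a given parent", so a session that was never held leaves no rating. No passage names a count of modules or consultations by wave.

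The 2-month wave is one of the two of main interest and supplies the mediator. A weak result there could mean that the programme does not work or that little of it had yet been delivered. The waitlist arm raises a similar question at 6 months, because it is offered the programme only after the 4-month assessment.

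**Working it through.** **1. Reproduce the stated minimum.** Inputs: 5 modules and 1 consultation per module (FCU intervention protocol). 5 × 1 = 5, which equals the figure of at least 5 in the Pilot Study text. The two accounts agree on the count.

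**2. Size of the alternative reading.** At about 20 minutes a session, five sessions are 5 × 20 = 100 minutes and one session is 1 × 20 = 20 minutes. Counting the initial consultant session as well, the comparison is 5 + 1 = 6 against 1 + 1 = 2. To reach the lower figure a reader must set aside two sentences in the same paragraph: the one giving a consultation for every module, and the one having the consultant arrange the contact about the next module. Read with those, the additional meetings are most naturally extra to the module cycle.

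**3. Is the spread at 2 months caused by the wording?** Let *m* be the modules a family has completed by 2 months, from 0 to 5.

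- Pilot Study text: one session follows each completed module, so sessions = *m*, a range of 0 to 5.
- FCU intervention protocol: the same, except that a family with *m* = 0 is due a check-in once 2 months have passed.

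The range is 0 to 5 post-module consultations under either text. Self-pacing produces it.

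**4. Timing against the 2-month post-test.** If completion means all five modules, a family would need one module and its consultation about every 61/5 = 12.2 days to finish in 2 months (59/5 = 11.8 to 62/5 = 12.4, depending on the calendar months). If completion means the interview, assessment and feedback of the original FCU, no such pace is implied. On the first reading the introductory sentence cannot be true of every family at 2 months. The start of the 2-month limit is not stated either. If it runs from the initial session, which follows baseline, its end falls after the 2-month post-test.

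**5. What in the analysis uses these quantities?**

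| Planned element | Depends on sessions held or on completion? |
|---|---|
| Post-test dates | No: 2, 4 and 6 months from baseline |
| Wave-specific regressions | No: assigned arm and baseline value |
| Growth models | No: assigned arm predicts rate of change |
| Mediation, 2-month mediator to 4-month outcome | No: waves are named |
| Engagement summary | Descriptive and open-ended |

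**6. Waitlist arm.** The programme is offered after the 4-month assessment and participation ends at 6 months. If the same limit applied to this arm, 4 + 2 = 6 months, so again 0 to 5 consultations are possible by the last assessment. The plan already expects smaller differences at 6 months for this reason.

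**The case for a change.** The strongest case for acting rests on timing. Even on the narrow reading of completion, the feedback discussion can fall at or after the first post-test. The triggers also differ: for a parent who never finishes the first module, the Pilot Study text calls for no check-in, while the FCU intervention protocol calls for one at 2 months. Feasibility is a stated goal of Aim 2, and how much was delivered is central to it. Session recordings are kept only for the duration of the study (Section F), so counts are easier to recover early. Youth follow-up exists only at 6 months, when the waitlist arm may have had some of the programme.

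Part of this stands. What the additional meetings are additional to is not spelled out, completion is undefined, the triggers differ, and no count by wave is named. These are differences of description. Naming a wave for the post-treatment effect would add little, because the Data analytic plan already names 2 and 4 months and fixes the mediation sequence. The lack of earlier youth data is a separate matter that rewording these sentences would not touch.

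The fear that consultants would work to different minimums has no support in the text. A lead consultant oversees training and supervision, guidance is repeated quarterly, and a licensed psychologist supervises. The counts fit within the planned engagement summary, and the 2-month satisfaction survey already asks about "factors related to uptake and usage of the information".

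**Conclusion.** No change to the plan follows. The supposed gap of 5 sessions against 1 depends on a strained reading; the two accounts agree on 5. The possible range of 0 to 5 consultations at 2 months belongs to a self-paced programme and would remain under any wording. An analysis by assigned arm at dates fixed from baseline estimates the effect of offering the programme by that date, and it is valid whatever the exposure. There is no effect on type I error or on the planned estimates.

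What remains is clerical: an unanchored word, an undefined completion point, and a time limit that appears in only one account. These passages need reconciling when delivery is described, and nothing here says which rule is right. The phase table in Section C lists the pilot as completed, so new wording could not alter what families received. Analysts can be expected to state the rule that was applied and, where records allow, to give modules and consultations by wave in the summary already planned.

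This conclusion assumes that the assigned-arm analyses are run as written. The documents do not say how many families had little contact by 2 months or whether dated app logs were kept. Both affect how fully delivery can be described, and neither affects the planned models.
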